2.3 Data Acquisition

File path for raw data: ..\CRU\Pulmonary\[name]\Pro00101848 mCST Blueprint\Main Analysis\DATA\RAW

File Name	Description
Blueprint Data Export XXXX.xlsx	Blueprint App data pulled by [name] This file has multiple sheets.
BlueprintScreeningAn_SAS_xxxx	Blueprint REDCap data pulled by [name]

Note: Data will be analyzed in SAS 9.4.

3 Outcomes, Exposures, and Variables of Interest

3.1 Primary Outcome(s)

Variable	Dataset	Description	Specifications

hads	Blueprint/Baseline	HADS total score at T0	Continuous
Hads	Blueprint/T1	HADS total score at T1	Continuous (may need to be derived from item scores HADS01—HADS14)
Score_hads	Blueprint/T2	HADS total score at T2	Continuous (may need to be derived from item scores HADS01—HADS14)
Score_hads	Blueprint/T3	HADS total score at T3	Continuous (may need to be derived from item scores HADS01—HADS14)
ptss	Blueprint/T1	PTSS total score at T1	Continuous (may need to be derived from item scores ptss_1—ptss_10)
Score_ptss	Blueprint/T2	PTSS total score at T2	Continuous (may need to be derived from item scores ptss_1—ptss_10)
Score_ptss	Blueprint/T3	PTSS total score at T3	Continuous (may need to be derived from item scores ptss_1—ptss_10)
D3mo_HADS	Blueprint/T3 Blueprint/T1	Change in HADS at 3 months	Derived as Score_hads(T3) - ???
D1mo_HADS	Blueprint/T2 Blueprint/T1	Change in HADS at 1 months	Derived as Score_hads(T2) - ???
D3mo_PTSS	Blueprint/T3 Blueprint/T1	Change in PTSS at 3 months	Derived as Score_ptss(T3) - ???
D1mo_PTSS	Blueprint/T2 Blueprint/T1	Change in PTSS at 1 months	Derived as Score_ptss(T2) - ???
ADLs/IADLs	T1, t2, t3		Not really an outcome but...
Systems Usability Scale	T1		
PHQ-10 physical symptom scale	T1, t2, t3		
Quality of life 100-point VAS	T1, t2, t3		
List		Feasibility	
Eligibility: 70% of positive screens Consent: 80% of eligible Randomized: 80% of consented Retention: 80% Adherence: 75% of tasks
 
***note that these need to be defined a bit more specifically

CSQ-8	`	Acceptability	

3.2 Primary Exposure(s)

Variable	Dataset	Description	Specifications
Plan_name	Blueprint/Participants	Trial Arm	
A multi-level categorical variable
 
- Blueprint Screening & Baseline: Exclude- Blueprint (Group 1): Arm 1- Blueprint (Group 2): Arm 2- Blueprint (Control): Arm 3

3.3 Other Variables of interest

Variable	Dataset	Description	Specifications

4 Statistical Analysis Plan

All analyses will be done using SAS 9.4. Continuous variables will be summarized with mean/standard deviation/median/Q1-Q3/range and categorical variables with frequency counts and percentages. Number of missing data for each variable will be reported.

4.1 Analysis Plan for Primary Aim 1

1. First, we will describe our cohort. In Table 1 we will summarize participant characteristics overall and by arm. No statistical tests will be provided as this was a randomized trial, and ideally groups should be balanced.
2. To assess Aim 1 for feasibility and acceptability we will evaluate CSQ-8 and SUS scores. Results will be reported in Table 2.

4.2 Analysis Plan for Primary Aim 2

1. To address Aim 2, we will describe the secondary outcomes at each time point by arm, as well as the change in scores at T2 and T3 from T1 in Table 3. Any additional secondary outcomes will be described in this table.
2. To assess if there was change at each timepoint of interest between the arms we estimate mean changes (and 95% CI) from baseline to each timepoint for each distress outcome (HADS, PTSS) using a general linear model (PROC MIXED). Model parameters will include treatment arm (1, 2, 3), time indicator (T1, T2, T3), and an arm by time interaction term. Change estimates and CI's will be reported in Table 4. To quantify clinically important differences, rather than report p-values which is not recommended for pilot studies with

small sample sizes, we will compare the estimated group mean differences and 95% CI's to half (0.5) of the baseline standard deviation (SD) of each outcome score.

5 Appendix I: Planned figures and tables

Figure 1: CONSORT Diagram

Table 1: Demographic characteristics of participants at baseline

Characteristic	Arm 1: Intervention Group 1 (Blueprint + Therapist) N=	Arm 2: Intervention Group 2 (Blueprint only) N=	Arm 3: Control (Usual Care) N=	Total N=
Stratification Variables				
Age				
<50				
≥50				
ICU Service				
Medical				
Surgical				
Baseline HADS				
<14				
≥14				
Other Baseline Characteristics				
Age				
Mean (sd)				
Median				
Q1, Q3				
Range				
Gender				
Male				
Female				

Table 2: Feasibility and Acceptability

Characteristic	Arm 1: Intervention Group 1	Arm 2: Intervention Group 2	Arm 3: Control (Usual Care)	Total N=

	(Blueprint + Blueprint Therapist) N=		N=
	N=	N=	
Feasibility			
% Consented	--	--	--
% Randomized	--	--	--
% Retained			
% Completed Surveys			
T1			
T2			
T3			
All timepoints			
% Completed all intervention components		--	--
Acceptability			
CSQ Score			

Table 3: Participant Outcomes

Characteristic	Arm 1:	Arm 2:	Intervention Arm 3: Group 1 (Blueprint + Blueprint Therapist) N=	Control (Usual Care) N=	Total N=
	Intervention	Intervention			
	Group 1 (Blueprint + Blueprint Therapist) N=	Group 2 (Blueprint only) N=			
Hospital LOS (Discharge - admission)					
Hospital discharge disposition					
3 month disposition					

Table 4: Observed and Estimated mean score and differences by Arm and Time for HADS and PTSS outcomes

	Baseline (T1?)	1 Month (T2)	3 Months (T3)	Δ 1 month - Baseline	Δ 3 months- Baseline
HADS					
Observed Score					
Arm 1 (BP + Therapist)					
Arm 2 (BP only)					
Arm 3 (Control)					
Estimated Mean Score (95% CI)					
Arm 1 (BP + Therapist)					
Arm 2 (BP only)					

Arm 3 (Control)					
Diff (Arm 1 - Arm 3)					
Diff (Arm 2 - Arm 3)					
PTSS					
Observed Score					
Arm 1 (BP + Therapist)					
Arm 2 (BP only)					
Arm 3 (Control)					
Estimated Mean Score (95% CI)					
Arm 1 (BP + Therapist)					
Arm 2 (BP only)					
Arm 3 (Control)					
Diff (Arm 1 - Arm 3)					
Diff (Arm 2 - Arm 3)

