## 9. Statistical Design, Analyses Plan, and Sample Size and Power

### Statistical Design and Analyses Plan

The primary goal of this 3-arm pilot RCT is to explore the feasibility and acceptability of mCST to inform a definitive future clinical trial. To do so, we will test differences between observed and a priori-defined benchmarks among mCST recipients using t-tests for continuous variables and chi-square tests for categorical variables.

The secondary goal is to estimate a reasonable range of clinical effect of mCST in comparison to a usual care control condition. General linear models will be used to estimate mean changes and corresponding 95% confidence intervals (CIs) in psychological distress (i.e., HADS and PTSS scores) for each treatment group over the 3 months of post-randomization follow-up using SAS PROC MIXED (SAS Institute, Cary NC). We will fit the models with an unstructured covariance matrix to better understand and represent the correlation between patients' repeated measures. We will also use similar modeling strategies to explore how the key clinical characteristics (e.g., history of ICU delirium, illness severity, diagnosis grouping), objective physical characteristics (e.g., functional status), sociodemographic factors, and mechanistic elements (e.g. self-efficacy) described in the conceptual model are associated with changes in psychological distress both within and between treatment groups. While for main analyses we will pool all mCST participants in comparisons with usual care control, we will also perform exploratory analyses similar to those described above to compare all three groups as well.

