1.1 Study Aims

1.1.1 Primary Aim 1

Determine the feasibility and acceptability of the Blueprint app.

1.1.2 Primary Aim 2

Determine the clinical impact on ICU survivors' 1 and 3 month psychological distress symptoms of intervention groups compared to usual care control.

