1.2 Study Hypotheses

1.2.1 Primary Hypothesis 1

The primary hypothesis is that the mobile CST app 'Blueprint' will be feasible and acceptable based on comparison of observed to a priori benchmarks.

1.2.2 Primary Hypothesis 2

The secondary hypothesis is, compared to usual care, the intervention participants will have improvement in symptoms of psychological distress (HADS and PTSS scores) at the 1 and 3 month timepoints (T2 and T3).

2 Study Design and Study Population

Participants are patients who were admitted to the ICU and were critically ill with either respiratory failure/insufficiency or cardiac failure/insufficiency. Additionally, participants experienced a high level of distress (HADS ≥ 8) at baseline.

This is a randomized clinical trial, where participants are consented and randomized to 1 of 3 arms (2 intervention arms, 1 control arm) in a 1:1:1 ratio. A total randomized sample size of 45 participants (15 per arm) was targeted. A method of minimization was used for randomization, with the aim to balance 3 stratification characteristics: ICU service (medical, surgical), baseline HADS score (<14 , ≥ 14), and age (<50 , ≥ 50).

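### The SAP does not plan the protocol's main clinical-effect estimate, all app (mCST) participants pooled against usual care, and does not declare the departure

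*SAP*

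**What the plan says.** **Protocol, section 9.** The secondary goal is to "estimate a reasonable range of clinical effect of mCST in comparison to a usual care control condition". For this, "for main analyses we will pool all mCST participants in comparisons with usual care control", and then "we will also perform exploratory analyses similar to those described above to compare all three groups as well". The repeated-measures models are to be run in PROC MIXED, and the protocol will "fit the models with an unstructured covariance matrix".

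**SAP, aims and hypotheses.** Aim 2 (1.1.2) refers to "intervention groups compared to usual care control", which fits either a pooled or an arm-level comparison. Hypothesis 2 (1.2.2) reads more like the pooled one: "compared to usual care, the intervention participants will have improvement in symptoms of psychological distress".

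**SAP, analysis.** Section 3.2 defines the exposure as "A multi-level categorical variable" with Arms 1, 2 and 3. Section 4.2 item 2 says: "Model parameters will include treatment arm (1, 2, 3), time indicator (T1, T2, T3), and an arm by time interaction term". Estimated differences and CIs are to be compared with half the baseline SD, without p-values. For each outcome, Table 4 has a row for each arm and two difference rows, Arm 1 − Arm 3 and Arm 2 − Arm 3. The SAP contains no pooled variable, contrast or row. Its log has a creation entry only.

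**The concern.** The comparison that the protocol calls exploratory is the only one the SAP plans, and the comparison that the protocol calls main is absent. An analyst who follows the SAP literally will not produce the estimate the protocol promises for the design of the definitive trial.

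Table 4 would show eight differences in change with none ranked first. With no p-values planned, a prior ranking of the estimates is the main protection against choosing the headline result after seeing the data.

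**Working it through.** The documents give no precision or power figure for this comparison, so there is nothing of the plan's own to reproduce. The check sets the texts side by side and then sizes the consequence.

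**Texts**

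| | Protocol section 9 | SAP 3.2, 4.2, Table 4 |
|---|---|---|
| Arms 1+2 versus usual care | main | not planned |
| Arm-level comparisons | exploratory | the only ones planned, unranked |
| Covariance | unstructured | not stated |
| Departure declared | n/a | no |

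**Number of estimates.** Table 4: 2 contrasts × 2 change columns × 2 outcomes = 8. The protocol's main analysis: 1 × 2 × 2 = 4.

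**Precision.** Inputs: 15:15:15 (SAP section 2) and 25:25:10 (Protocol section 2). Assumptions: equal SD of change in all arms and complete data. Results are in SD-of-change units.

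- Single-arm SE = sqrt(1/n₁ + 1/n₃). Pooled SE = sqrt(1/(n₁+n₂) + 1/n₃). Half-width = t(0.975, N−3) × SE.
- 15:15:15, 42 df: single sqrt(1/15 + 1/15) = 0.365, half-width 0.74; pooled sqrt(1/30 + 1/15) = 0.316, half-width 0.64. Ratio 0.866, so the pooled SE is 13% smaller.
- 25:25:10, 57 df: single sqrt(1/25 + 1/10) = 0.374, half-width 0.75; pooled sqrt(1/50 + 1/10) = 0.346, half-width 0.69. Ratio 0.926, so 7% smaller.

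These are different contrasts. Adding the pooled row does not make the single-arm rows more precise.

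**Is the information lost?** No. The pooled change is (Arm 1 + Arm 2)/2 − Arm 3. With equal weights its SE is sqrt(SE₁²/4 + SE₂²/4 + SE₃²), taken from the arm rows. In generalised least squares with known covariance this matched the model's pooled SE to rounding error, both with complete data and with 20% missing at T2 and T3.

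**Arm weights.** Equal and participant weights coincide when Arms 1 and 2 are the same size. As an assumed example, suppose 15, 10 and 15 are analysed. Participant weights are then 15/25 = 0.60 and 10/25 = 0.40, and the estimate moves by 0.60 − 0.50 = 0.10 times the Arm 1 − Arm 2 difference. The SE is sqrt(1/25 + 1/15) = 0.327 with participant weights and sqrt(0.25/15 + 0.25/10 + 1/15) = 0.329 with equal weights.

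**The case against.** **The table shells are unfinished.** SAP 4.1 sends the usability score to Table 2, which has no row for it. SAP 4.2 sends change scores to Table 3, which lists only length of stay and dispositions. A missing row is therefore weak evidence that pooling was rejected, and the three-level model can yield the pooled contrast. This is fair as to intent, but neither the text of 4.2 nor the table asks for the estimate.

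**The documents may not be matched versions.** They also differ on sample size, allocation and care setting. That may explain the mismatch, but it does not supply the missing analysis.

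**The stakes are modest.** Distress is secondary (Protocol section 4), efficacy is not being tested (section 9), and the fix raises the count of differences from eight to twelve. This stands, and it is why the point is called a reporting gap. The gain is that four of the twelve would be designated in advance.

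**The magnitudes depend on scale and retention.** This also stands.
- The SAP's yardstick is half the baseline SD. With equal SDs the two scales agree only at a T1–follow-up correlation of 0.5. At 0.7 the factor is sqrt(2 × 0.3) = 0.775, so 0.74 and 0.64 become 0.57 and 0.49 baseline SD.
- At the 80% retention benchmark (12 per arm), the half-widths are 0.83 and 0.72 in SD-of-change units.
- Strict 3:3:2 of 60 is 22.5:22.5:15, not 25:25:10. The SEs would be 0.333 and 0.298, 11% smaller when pooled.

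**The direct therapist question is Arm 1 − Arm 2, which Table 4 also lacks.** This is true and is a reasonable further exploratory row.

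**Participant weights are ambiguous under dropout.** This is also true, so the SAP must say which counts define them.

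**Conclusion.** The concern holds. Protocol section 9 and SAP 4.2 with Table 4 conflict on which comparison is the main one for HADS and PTSS. Followed as written, the SAP omits the protocol's main clinical-effect estimate and ranks nothing in its place.

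This conclusion rests on the texts and does not depend on precision. The precision figures show only a moderate difference: the pooled SE is 13% smaller at 15:15:15 and 7% smaller at 25:25:10, assuming equal SDs and complete data. No test is invalidated and the pooled estimate can be rebuilt from the arm rows. What is missing is its pre-specified place as the main estimate. The SAP should be corrected.

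**What to change.** 1. In SAP 4.2, name the pooled mCST − usual care difference in change from T1, at T2 and at T3, as the main Aim 2 estimate for HADS and PTSS. Obtain it by ESTIMATE statements from the same PROC MIXED model, with the protocol's unstructured covariance stated.
2. State the arm weights. Participant weights follow the protocol's wording most literally, and the counts they use must be given. Equal weights are the alternative.
3. Make the pooled difference the first difference row of Table 4 for each outcome. Keep the two arm-versus-control rows, labelled exploratory.
4. If the arm-level contrasts are meant to be the main ones, say so and give the reason for departing from Protocol section 9.
5. State T1 as the baseline for change. SAP 3.1 leaves the subtracted term open and Table 4 queries it. The SAP overview does label T0 as baseline, but 4.2 item 1, the dataset column in 3.1 and the T1 eligibility score all point to T1, and 3.1 has no T0 row for PTSS.

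**Cost.** Two ESTIMATE statements and one table row per outcome, and one or two sentences of text. There is no new data collection and no change to the model. The drawback is that the pooled estimate averages app-plus-call with app-only. The balance between therapist and app is a question the pilot is meant to inform (Protocol section 2), so the arm-level rows must stay.

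**Separate and optional.** T1 precedes randomisation, so T1 means could be constrained equal across arms, or T1 used as a covariate. With equal SDs the SE is multiplied by sqrt((1+ρ)/2): 0.866 at an assumed correlation of 0.5 and 0.922 at 0.7. The gain is smaller, about 3–8% in simulation under assumed score distributions, once T1 is truncated by the HADS ≥ 8 entry rule. Age and ICU service belong only with that step: as main effects in the current model they leave the change contrasts unchanged with complete data.

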### 2. Background

As survival has improved for the 2 million people with cardiorespiratory failure managed annually in the US, it has become apparent that these patients suffer from severe and persistent post-discharge symptoms of psychological distress including depression, anxiety, and post-traumatic stress disorder (PTSD). However, few targeted interventions exist that are relevant to patients' experiences and that accommodate their many physical, and social barriers to personalized care. To fill this gap, we have developed an innovative, native mobile coping skills training (CST) program that promotes automated care delivery and self-management of symptom-related distress. CST, by improving self-efficacy and adaptive coping, reduces psychological distress symptoms, thereby also improving quality of life.

Previous trials, in which this pilot randomized clinical trial (RCT) is based, have demonstrated that adaptive coping skills training (CST), is an active response for managing stressful events such as the experience of a critical illness. Cardiorespiratory failure survivors have emphasized in their own words the importance of coping to their perceived quality of life. While the use of adaptive coping skills (e.g., relaxation, positive reframing, problem solving) is associated with decreased psychological distress, survivors infrequently apply such strategies.

Therefore, we propose a 2-year project that will pilot CST via a native mobile app known as "Blueprint" in which 2 distinct aims will be operationalized and tested. Aim 1 focuses on usability prior to release for real patient use. For aim 1, 5 to 15 subjects will be recruited and enrolled and provide feedback on app use. Aim 2, which is the main focus of this project, is an RCT in which 60 eligible patients will be randomized to 1 of 3 arms in a 3:3:2 manner (i.e., n=25: n=25: n=10). The pilot RCT is both necessary and sufficient to inform a future definitive RCT designed to test a longer-term, self-directed mobile app version of CST. The pilot will ultimately aid in addressing key gaps identified in previous trials (CSTEP and LIFT RCTs). Both trials previously conducted raised questions about the ideal balance between the uses of a CST therapist versus the use of an app to deliver content. At the conclusion of this pilot study, we hope to have addressed the key questions raised in previous work and use the learned information to inform the conduct of a next-step multi-center RCT.

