## Study Visits

For aim 1, each participant will be asked to complete a singular study visit that last approximately 30-60 minutes. During this study visit, post consent, the individual will be asked to do the following:

- Find and install the Pattern Health app
- Register to the Blueprint study
- Complete baseline survey
- Randomize to 1 of 3 arms or screen fail purposely
- Provide feedback on app content and usability.

For aim 2, each consented patient will be asked to complete up to four individual study visits.

- **Baseline:** this visit is to occur post-consent (same day, ideally) at the time of hospital admission just prior to discharge. However, this visit may occur at the time of hospital discharge within 1-3 days of returning to home. At this visit, the following will occur:
  - App Registration
  - Baseline Survey Completion
- **T1 (Day 0) (+30 days):** this visit is to occur at the time of hospital discharge to home, ideally within the first week (7 days) of returning to home; however, it can occur up to 1 month (30 days) from the time of hospital discharge to home. At this visit, the patient will complete the T1 survey via the app, which includes the HADS, PTSS, and PHQ-10 surveys. Score dependent, the patient will be randomized to 1 of 3 arms: Group 1 (Blueprint app), Group 2 (Blueprint app + therapist), and Group 3 (control; no Blueprint app and no therapist). If the patient's psychological distress score is too low; he/she will receive an automated alert via the app describing they are not eligible and their study participation is complete.
- **T2 (Day 30) (+60 days):** this visit is to occur post 1 month randomization for those patients who remain eligible to participate in the study. HADS, PTSS, and PHQ-10 surveys will be administered again. If the patient's survey scores indicate high levels of distress, as defined by a triggered SI alert or increased distress score from T1, a delegated study team member will contact the patient for safety precautions.

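### SAP 4.2 compares arms on change from T1 without using the fact that T1 precedes randomisation: valid on average, but less precise than a T1-adjusted contrast and shifted by any chance T1 imbalance

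*SAP*

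**What the plan says.** Protocol section 9 states: "General linear models will be used to estimate mean changes and corresponding 95% confidence intervals (CIs", for HADS and PTSS, by treatment group, in PROC MIXED with an unstructured covariance matrix. SAP 4.2 item 2 repeats the aim ("we estimate mean changes (and 95% CI) from baseline to each timepoint for each distress outcome (HADS, PTSS") and gives the mean structure: "Model parameters will include treatment arm (1, 2, 3), time indicator (T1, T2, T3), and an arm by time interaction term". The SAP does not mention the covariance.

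Table 4 of the SAP has rows for Arm 1 minus Arm 3 and Arm 2 minus Arm 3 under every column, including the baseline column and the two change columns. These differences and their 95% intervals are to be compared with half a baseline SD, without p-values.

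The reference for change is T1 in SAP 4.2 item 1 ("the change in scores at T2 and T3 from T1 in Table 3"). Elsewhere it is unsettled: Table 4 puts a question mark after T1, and the derivation in SAP 3.1 that begins "Derived as Score_hads(T3" ends in question marks where the baseline should stand.

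T1 comes before allocation. Protocol section 7, Study Visits, says of the T1 visit: "Score dependent, the patient will be randomized to 1 of 3 arms". The definition of a randomised patient in the same section requires a completed T1 survey. Neither document enters T1 as a covariate or sets a common T1 mean.

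**The concern.** Arm by three times with all interactions is nine free means. With complete data and an unstructured covariance, the arm-by-time contrast in this model is the raw difference in change scores. It lets the T1 means differ by arm, although randomisation makes the true means equal and any observed T1 difference is chance.

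There are two consequences. The interval is wider than the same data allow unless follow-up tracks T1 almost one for one. And once the arms happen to differ at T1, the change score over-corrects for that difference.

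This matters here because the interval is the product. Protocol section 9 says that the trial is not meant to test efficacy and that the secondary goal is a reasonable range of effect, while the control arm is small: 15 in the SAP ("A total randomized sample size of 45 participants (15 per arm) was targeted") or 10 in the Protocol ("60 eligible patients will be randomized to 1 of 3 arms in a 3:3:2 manner (i.e., n=25: n=25: n=10").

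**Working it through.** **The plan's own figure.** There is none to reproduce. 3 x 15 = 45 adds up, but no SD, correlation, effect size or interval width is given.

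**Inputs.** From the SAP: 15 per arm, the mean structure above, and the 0.5 SD yardstick. Assumed, because the documents are silent: the correlation rho between T1 and follow-up (0.3 to 0.8) and the ratio r = SD(follow-up)/SD(T1) (1.0, varied to 0.9 and 1.2). The slope of follow-up on T1 is rho x r. Widths are in T1 SD units.

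**Formulas**, with k = 1/15 + 1/15 = 0.1333:
- Difference in change: variance = (1 + r² - 2 rho r) k, t on 42 df (2.018).
- T1-adjusted: variance = r²(1 - rho²) k x (1 + 1/40), t on 41 df (2.020). The factor 1 + 1/40 is the small-sample price of estimating the slope.
- Apart from that factor, the first variance exceeds the second by (1 - rho r)² k, which is never negative and is zero when rho r = 1.

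**Worked case, rho 0.5, r 1.** Change: 2.018 x sqrt(1.0 x 0.1333) = 0.737. Adjusted: 2.020 x sqrt(0.75 x 0.1333 x 1.025) = 0.647. The adjusted interval is 12% narrower.

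| r | rho | Change half-width | Adjusted half-width | Adjusted v change |
|---|---|---|---|---|
| 1.0 | 0.3 | 0.872 | 0.712 | 18% narrower |
| 1.0 | 0.5 | 0.737 | 0.647 | 12% narrower |
| 1.0 | 0.7 | 0.571 | 0.533 | 7% narrower |
| 1.0 | 0.8 | 0.466 | 0.448 | 4% narrower |
| 1.2 | 0.3 | 0.966 | 0.855 | 12% narrower |
| 1.2 | 0.5 | 0.821 | 0.776 | 5% narrower |
| 1.2 | 0.7 | 0.642 | 0.640 | no real gain |
| 1.2 | 0.8 | 0.531 | 0.538 | 1% wider |

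With r = 0.9 the gain is larger: 0.703 to 0.582 at rho 0.5, 17% narrower.

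**Simulation**, 10,000 three-arm trials of 15 per arm, r = 1. Mean half-widths, change v adjusted, were 0.867 v 0.707, 0.732 v 0.642 and 0.567 v 0.530 at rho 0.3, 0.5 and 0.7. Both methods had coverage between 94.9% and 95.2% and a mean error of about zero.

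**Other settings, rho 0.5, r 1.** Protocol allocation, 25 v 10: 0.749 v 0.655. With about 13% missing at T2 and 20% at T3, known covariance: 0.756 v 0.666 at T2 and 0.777 v 0.690 at T3. The adjusted intervals are 11% to 13% narrower.

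**HADS.** Entry at HADS 8 or more shrinks the T1 variance to a fraction v, so there is less to gain. The variance ratio, adjusted to change, is (1 - rho²)/[(1 - rho²) + (1 - rho)² v]. For an assumed uncut mean/SD from 12/6 to 16/7, v runs from 0.53 to 0.67. The ratio is then 0.78 to 0.73, 0.85 to 0.82 and 0.91 to 0.89 at rho 0.3, 0.5 and 0.7. Taking square roots and applying the small-sample factor, intervals are about 11-13%, 7-8% and 3-4% narrower.

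**Shift given a T1 imbalance d.** The change estimate moves by -(1 - rho r) d. In the simulation it moved by -0.70, -0.48 and -0.30 per SD of imbalance; the adjusted estimate moved by about 0. Under simple randomisation d has SD sqrt(0.1333) = 0.37. A one-SD imbalance therefore shifts the change estimate by 0.26, 0.18 or 0.11 SD at rho 0.3, 0.5 or 0.7. For HADS, minimisation at 14 limits d: exact balance on a median split of a normal score would cut its SD to about 0.22, and the shift at rho 0.5 to 0.22 x 0.5 = 0.11 SD. PTSS is not a minimisation factor.

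**The case against.** The strongest reply is that nothing is wrong with the planned inference. Averaged over randomisations the change contrast is unbiased, and its interval already allows for chance T1 differences. That stands. A reader might infer from the shift that the SAP analysis is biased or invalid; the shift exists only conditional on the imbalance that happens to occur, and coverage is correct.

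The size is also easy to overstate. At correlation 0.5 with equal SDs, the large-sample variance ratio 2/(1 + rho) = 1.33 suggests a gain worth a third more patients. With 15 per arm it is (0.737/0.647)² = 1.30, the HADS gain is smaller, and if scores spread out after T1 the gain can vanish.

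Nor does adjustment rescue the comparison with the yardstick. At correlation 0.5 the adjusted half-width of 0.65 SD still exceeds 0.5 SD. The distress comparison is a secondary goal in the Protocol, and no test is planned.

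One could also read the planned group mean differences as raw differences at T2 or T3. T1 is then still unused: at correlation 0.5 and equal SDs the half-width is again 0.74 against 0.65.

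Finally, using T2 and T3 as the only responses would drop the modelled within-arm changes that both documents promise. That limits the remedy; it does not answer the point.

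The question marks over the baseline are a separate gap and no evidence for this one.

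**Conclusion.** The point holds as one of efficiency and of sensitivity to chance imbalance. SAP 4.2 item 2 ignores a baseline that every randomised patient has and whose true mean is equal across arms. The direction is secure; the size is not, because it rests on a correlation and an SD ratio that the documents do not give.

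For 15 per arm, the plausible gain in interval width runs from about a fifth (correlation 0.3, equal SDs) down to nothing (correlation 0.7, follow-up SD 1.2 times T1 SD). HADS gains less than PTSS, on the assumed T1 distributions. The conditional shift can reach a notable share of the yardstick: at correlation 0.5 a one-SD PTSS imbalance moves the estimate by 0.18 SD, over a third of 0.5 SD. For HADS it is reduced but not removed; the SAP does not say whether the HADS score used for minimisation is T0 or T1.

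The change is worth making before arm-level results are seen, because it uses data already collected. It does not correct an invalid analysis.

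**What to change.** In SAP 4.2 item 2:
- Keep T1, T2 and T3 as responses in the same PROC MIXED model, and state the unstructured covariance of Protocol section 9.
- Constrain T1 to one mean common to all arms: drop the arm main effect and keep arm-by-time terms at T2 and T3 only.
- Report arm differences at T2 and T3 with 95% intervals against the 0.5 SD yardstick.

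In Table 4, keep the model-based within-arm changes from T1 and remove the model-based arm differences from the T1 column. Name T1 as the baseline there and in the SAP 3.1 derivations, so that they match SAP 4.2 item 1.

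An acceptable alternative for the arm differences is a model with T2 and T3 as responses and T1 and T1-by-time as covariates. On its own it does not give the modelled within-arm changes.

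The cost is minor SAP and table edits and no new data. At worst the interval is about 1% wider, when correlation times SD ratio is near 1.
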